2 INTRODUCTION

2.1 STUDY RATIONALE

Total Knee Arthroplasty (TKA) has become a rapid recovery surgery. Hospital stays are shorter with rehabilitation done either in an acute (AR), sub-acute (SAR) rehabilitation center, or at home. Therefore, the surgeon and the surgical team are only apprised of the patients' progress during routine postoperative office visits done at 2 and 8 weeks. This could potentially result in a delay of treatment for any complications related to surgery.

Following discharge from the hospital approximately 41% of TKA patients are transferred to an AR or SAR for further rehabilitation. The length of stay in these facilities varies greatly. The use of a monitoring device would allow the surgical team to remotely monitor the patient criteria for a safe discharge. This criteria includes ambulation of 150 feet, ability to climb stairs and the bending of the knee to 110 degrees. Therefore, the X4 brace could alert the surgical team of patients who are failing to progress as expected.

Home based programs require the patient perform prescribed exercise regimens twice a day. One regimen is done with the guidance of a physical therapist (PT). The second therapy is done by the patient without supervision. Though home based exercises are convenient, assuring patient compliance with these prescribed exercise regimens is unknown. Transition to an outpatient rehabilitation puts an added burden on the patient as most will require someone to drive them. Outpatient rehabilitation is 3 times per week leaving the remainder of the exercises up to the patient.

Patients and their care team need a solution to ensure both the compliance and accuracy with the exercise regimen. Currently, there is no method for the surgical team to ensure patients are following the protocols and progressing as expected. The surgical team needs a solution which would provide them more timely access to patient recovery status, activity and level of compliance. Additionally, the use of this device could also provide needed security for a patient as they are aware their surgical team is monitoring their recovery.

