4 STUDY DESIGN

4.1 OVERALL DESIGN

Hypotheses: The X4 brace with the Motion Intelligence platform will provide an enhanced, cost-effective postoperative recovery following total knee arthroplasty (TKA).

This is a prospective, randomized clinical trial to evaluate the use of the X4 knee brace with the Motion Intelligence platform in patients having unilateral TKA. This brace is a FDA approved, marketed product being used as per the manufacturer's (DJO) marketed indications. Patients will be randomized to one to 4 cohorts:

This study is designed to determine if using a "virtual rehabilitation" device leads to enhanced recovery following total knee arthroplasty by improving patient objective and subjective outcome measures. These outcomes will be collected using a validated tool called the Knee Society Score (KSS)

(Appendix A). The KSS is a standard of care tool collected for all TKA patients pre-operatively and postoperatively at the 8 week visit.

- Cohort 1- Study group-Home discharge. Patients randomized to this group will be provided with the X4 brace and trained on the use of Motion Intelligence platform.
- Cohort 2- Control group-Home discharge. Patients randomized to this group will serve as the control group. There will be no changes to the standard of care recovery for a TKA patient.
- Cohort 3- Study group-Inpatient rehabilitation. Patients randomized to this group will be provided with the X4 brace and trained on the use of Motion Intelligence platform.
- Cohort 4- Control group-Inpatient rehabilitation. Patients randomized to this group will serve as the control group. There will be no changes to the standard of care recovery for a TKA patient.

No interim analysis is planned for this study. Randomization schedule will be done by the statistician via RedCap.

The DJO X4 brace will be provided to the patient at no cost. Study visits, hospitalization, inpatient and outpatient rehabilitation costs are standard of care and will be the responsibility of the patient. There will be no payment for participation in this study.

All study patients will complete a daily "Daily Patient Log" (Appendix B) starting the day after discharge from the hospital until postoperative day (POD) 56. This log will document the patient's location:

- o Rehabilitation center or
- Home physical therapy or
- Physical therapy center
- Hospital (re-admission)
- Return to work (if applicable)

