6 STUDY INTERVENTION

6.1 STUDY INTERVENTION(S) ADMINISTRATION

6.1.1 STUDY INTERVENTION DESCRIPTION

Patients will be consented for the study at any time during the preoperative period. Following the surgical procedure the inclusion/exclusion criteria will be confirmed. Patients meeting study inclusion/exclusion will be randomized via the REDCap system when their discharge location (home vs inpatient rehabilitation) has been confirmed. Patients randomized to the X4 brace arm of the study will be assisted with downloading the Motion Performance Platform and provided with the X4 brace during their hospital stay. The average length of stay in the hospital is 2 days. During the hospital stay the study team will work with the patient and family members to insure they are adequately trained in the use of the device and comfortable using the platform. Contact information will be provided for any issues or concerns.

PROCESS AND PATIENT ON-BOARDING

POST-OPERATIVE FOLLOWING RANDOMIZATION

Following randomization the patient will be shown how to apply brace and assisted in downloading the Motion Intelligence application from either the Apple iStore or Google Play. The patient will be assisted with pairing the device to the brace. The patient will be instructed on how to use the application and importance of using the application.

The patient will be educated to do their exercises twice a day, once in the morning and once in the afternoon. Additionally, the application screen will monitor their progress post-surgery by showing them how many steps they have taken in a day, their active time and average flexion and extension. If the patient would like to be reminded that they need to do their exercises, they can set up a reminder by going to the "Settings".

Exercise Program:

The Exercise program was developed by some Key Opinion Leaders based on common practice. The investigators have reviewed the program and are in agreement with this program. These exercises are completed throughout the 56 day program and are selected for predetermined time periods (days) after surgery (see exercise regime for details on timing):

- 1. Ankle Pumps / Ankle Circles
- 2. Isometric Quad Sets
- 3. Supine Heel Slides
- 4. Straight leg raise
- 5. Hamstring and Calf Stretch * Hold 10 Seconds*
- 6. Clamshells
- 7. Seated Heel Slides in Chair
- Seated Passive Knee Extension *Hold 30 Seconds*

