6.3 MEASURES TO MINIMIZE BIAS: RANDOMIZATION AND BLINDING

Randomization:

Prior to randomization, patients will be stratified according to discharge location (home, inpatient rehabilitation). Within each stratum, patients will be randomly assigned in a 1:1 ratio to the X4 brace with the Motion Intelligence platform or standard of care.

The Biostatistics Unit will develop a randomization procedure using a permuted block design within the REDCap system). Additional details of the procedure, including required record keeping, will be further developed upon approval of this protocol. The Biostatistics Unit has extensive experience in implementing and in producing detailed documentation for such procedures.

Blinding and Concealed Allocation

Due to the nature of the X4 brace, it is not possible to blind the investigators or the participants. The randomization assignment will be obtained from BRMS, after consent has been obtained, after it has been determined that the subject has met all inclusion/exclusion criteria, and after the discharge location has been determined.

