9.4.3 ANALYSIS OF THE SECONDARY ENDPOINT(S)

Secondary Outcomes: Efficacy

Outcomes for all patients regardless of discharge location:

The association between number of outpatient visits to a physical therapy center and intervention group will be examined using Poisson regression. Discharge location (home, inpatient rehabilitation) will also

be included in the model. If the interaction between intervention group and discharge location is significant, then pairwise comparisons of intervention group within each discharge location will be examined within the Poisson regression model. If the Poisson model does not fit the data well, alternative methods for count data will be considered.

Outcomes for patients discharged to inpatient rehabilitation:

Number of inpatient days in a rehabilitation center

The association between number of inpatient days in a rehabilitation center and intervention group will be examined using Poisson regression. If the Poisson model does not fit the data well, alternative methods for count data will be considered.

Outcomes for patients randomized to the X4 brace with the Motion Intelligence platform:

The association between patient satisfaction with the X4 brace, as measured by the SUS scale, and discharge location (home, inpatient rehabilitation) will be examined using the two sided, two sample t-test. If the usual assumptions required for the t-test are not met, either a suitable transformation, or an appropriate nonparametric method will be used.

The association between number of days of compliance and discharge location will be examined using Poisson regression. If the Poisson model does not fit the data well, alternative methods for count data will be considered.

The association between number of days of adherence and discharge location will be examined using Poisson regression. If the Poisson model does not fit the data well, alternative methods for count data will be considered.

Other outcomes:

Provider satisfaction with the X4 brace, as measured by the SUS scale will be described by calculating summary statistics (median, 25th percentile, 75th percentile, minimum and maximum).

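### The inpatient-days model has no covariate although acute and sub-acute centers are pooled: precision may be lost in a small stratum, without bias

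*Combined protocol and SAP*

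**What the plan says.** For patients discharged to inpatient rehabilitation, section 9.4.3 specifies: "The association between number of inpatient days in a rehabilitation center and intervention group will be examined using Poisson regression". Intervention group is the only term. The fallback changes the count method and adds no covariate: "If the Poisson model does not fit the data well, alternative methods for count data will be considered".

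The background in section 2.1 shows that this stratum contains two kinds of facility: "Following discharge from the hospital approximately 41% of TKA patients are transferred to an AR or SAR for further rehabilitation". It then says: "The length of stay in these facilities varies greatly".

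The rest of the plan treats the two kinds as one. Section 6.3 stratifies on two levels only, home or inpatient rehabilitation. Section 6.1.1 has patients "randomized via the REDCap system when their discharge location (home vs inpatient rehabilitation) has been confirmed". On the daily log, section 4.1 says "This log will document the patient's location", and the lists there and in section 8.1 show rehabilitation center as a single entry. The log form itself (Appendix B) is not in the text available.

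**The concern.** Inpatient days is one of the two measures that section 3 sets against the rehabilitation-cost objective. It is also the only between-arm efficacy model in the plan with no covariate. The ANCOVA in 9.4.2 includes the preoperative score and discharge location, and the outpatient-visits model in 9.4.3 includes discharge location. Within the inpatient stratum discharge location is constant, so it cannot reduce variance there. Facility type is the obvious finer factor.

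If mean stay differs between AR and SAR, that difference stays in the residual variation of a comparison that uses well under half of the 240 patients. A wider interval on a cost measure is what is at stake. If facility type is never recorded, the adjustment cannot be made later either.

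**Working it through.** **No planned figure to reproduce for this endpoint.** The only sizing is in section 9.2, for the KSS subjective score (10 points, SD 27.5, two-sided 0.05). It reproduces: 119 per group for 80% power, and power 0.801 by the exact t calculation at 120 per group. It says nothing about inpatient days.

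**Stratum size.** 240 × 0.41 = 98.4, so about 98 patients, or m = 49 per arm under 1:1 allocation. This holds only if the trial mirrors the share in section 2.1.

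**Assumptions, none from the documents.** AR/SAR mean stays of 10/10, 10/12, 10/15 and 10/20 days; share q = 0.5 in each type; dispersion φ = 3 within type; true rate ratio 0.80. With an even split it does not matter which type has the longer stay.

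**Formulas.** With overall mean μ and difference in mean stay d:

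- within-type variance W = φμ
- between-type variance B = q(1−q)d²
- unadjusted variance of the log rate ratio = 2(W + B)/(mμ²)
- adjusted variance = 2W/(mμ²) = 2φ/(mμ)
- ratio of the two = 1 + B/W
- power = Φ(|ln 0.80|/SE − 1.96)

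| Mean stays | μ | W | B | Variance ratio | Power without → with the term |
|---|---|---|---|---|---|
| 10/10 | 10.0 | 30.0 | 0 | 1.00 | 0.52 → 0.52 |
| 10/12 | 11.0 | 33.0 | 1.00 | 1.03 | 0.55 → 0.56 |
| 10/15 | 12.5 | 37.5 | 6.25 | 1.17 | 0.55 → 0.62 |
| 10/20 | 15.0 | 45.0 | 25.0 | 1.56 | 0.51 → 0.69 |

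**Sensitivity of the variance ratio** (10/12, 10/15, 10/20):

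- 20% in AR, φ = 3: 1.02, 1.10, 1.30
- even split, φ = 5: 1.02, 1.10, 1.33
- even split, φ = 1: 1.09, 1.50, 2.67

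**Chance imbalance is not a second harm.** The SD of the between-arm difference in AR share is √(2 × 0.25/49) = 0.101, about 10 percentage points. At 10/20 days this moves the log ratio by about 0.101 × 10/15 = 0.067. The adjusted SE is √(6/(49 × 15)) = 0.090 and the unadjusted SE is √(2 × 70/(49 × 225)) = 0.113. Since 0.090² + 0.067² ≈ 0.113², the imbalance is the same variance inflation already counted in the unadjusted SE.

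**Simulation** (1,500 runs per scenario, 49 per arm, quasi-Poisson errors). At φ = 3 with an even split, power went from 0.48 to 0.47 at 10/10, from 0.51 to 0.56 at 10/15 and from 0.46 to 0.64 at 10/20. Type I error was 0.041 to 0.057 with or without the term.

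**Overdispersion.** In the φ = 3 scenarios, plain Poisson standard errors without the term gave type I error of 0.26 to 0.35. The 0.26 arose at 10/10, where facility type has nothing to explain, so the covariate cannot cure this.

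**The case against.** The strongest objection is that the documents never say AR versus SAR is known before randomization. A reader might infer it from section 6.1.1, because the discharge location is confirmed by then. But that section and section 6.3 name only home or inpatient rehabilitation, and AR and SAR appear only in the background and the abbreviation list. The trial is open-label, so a facility type settled after allocation could be affected by the arm, and adjusting for it could bias a comparison that is now unbiased. This stands, and it makes the remedy conditional. It does not defeat the remedy: a planned destination recorded before the assignment is revealed is a valid baseline covariate, wherever the patient later goes.

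A reader might also infer that a chance AR/SAR imbalance could pass for a device effect. Under randomization it is already part of the unadjusted standard error, and the simulated type I error shows no inflation when the errors allow for overdispersion.

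Nor does section 2.1 say that stays differ between AR and SAR. The variation could lie between patients or between centers of one type, so the range of gain must start at zero. Finally, the 41% describes TKA patients generally. The eligibility criteria (smartphone access; no wheelchair use, chronic opioid use or impairment limiting rehabilitation) may change the trial's share.

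**Conclusion.** The point holds as a matter of precision. The model for inpatient days has no covariate, while the plan itself names two pooled facility types and describes widely varying stays. The effect estimate remains unbiased. In a stratum of about 98 patients, the unadjusted variance is 1.00 to 1.56 times the adjusted one under assumed mean stays of 10/10 to 10/20 days, an even split and dispersion 3. In power at a rate ratio of 0.80, that is between no gain and about 18 percentage points. All of these inputs are assumptions, apart from the 41% share and the total of 240, and the documents cannot narrow the range.

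This is a cheap improvement to a secondary endpoint for which the plan claims no power. Overdispersion is a separate and larger risk for the same model.

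**What to change.** Add a REDCap field for the planned facility type (AR or SAR), completed before the assignment is revealed. In section 9.4.3, prespecify that planned type, not the facility actually attended, as a covariate in the inpatient-days model, and name the adjusted arm effect as the reported result for this endpoint. State that if the planned type is not settled before allocation, it will not be used as a baseline covariate.

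The cost is one data field, one or two sentences and one degree of freedom, with nothing gained if stays do not differ by type. The term does not replace a prespecified way of handling overdispersion.

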9.4.4 SAFETY ANALYSES

Safety Outcomes:

Outcomes for patients randomized to the X4 brace regardless of discharge location

- Adverse events: Each subject will be categorized at the end of the study as having had one or more adverse events, or not having had any adverse events.
- Serious adverse events: Each subject will be categorized at the end of the study as having had one or more adverse events, or not having had any serious adverse events.

Not Applicable

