3 OBJECTIVES AND ENDPOINTS

OBJECTIVES	ENDPOINTS	JUSTIFICATION FOR ENDPOINTS
Primary		
 To determine if patient postoperative outcomes, measured by the Knee Society Score, are improved by using the X4 brace with the Motion Intelligence platform To monitor the study group for any device related adverse events 	 To compare the Knee Society Scores, both objective and subjective scores, done preoperatively and at 8 weeks postoperatively between the control and study groups To monitor the study group for any device related adverse events 	The Knee Society Score is a validated tool used for assessing outcome in total arthroplasty patients Patients will be followed to ensure there are no issues with the utilization of the X4 brace
Secondary		
 To determine if there is a reduction in the rehabilitation costs (inpatient or outpatient) by using the X4 brace with the Motion Intelligence platform 	 To compare the number of inpatient days in a rehabilitation center between the control and study groups To compare the number of outpatient visits to a physical therapy center between the control and study groups 	To evaluate if the X4 brace provides user- friendly, cost-effective, enhanced patient recovery following total knee arthroplasty
 To evaluate patients satisfaction with the X4 brace with the Motion Intelligence platform 	 To evaluate patient's satisfaction with the X4 brace with the Motion Intelligence platform via the "System Usability Scale" (SUS) questionnaire (study group only) 	
 To evaluate patients compliance and adherence using the X4 brace with the Motion Intelligence platform 	• To measure patient's compliance using the X4 brace with the Motion Intelligence platform by counting how many days they used the platform as prescribed within an 8 week period. A patient will be	

OBJECTIVES	ENDPOINTS	JUSTIFICATION FOR
		ENDPOINTS
	considered compliant if they use the platform once a day.	
	 To measure patient's adherence using the X4 brace with the Motion Intelligence platform. Adherence is defined as performing the entire exercise routine as prescribed once a day. 	
 To evaluate provider satisfaction using the X4 brace with the Motion Intelligence platform 	 To evaluate provider satisfaction with the X4 brace with the Motion Intelligence platform via the "System Usability Scale" (SUS) questionnaire (study group only) 	In order for this technology to become part a postoperative regime the platform should be both effective and user friendly for the provider

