8.3.3 CLASSIFICATION OF AN ADVERSE EVENT

8.3.3.1 SEVERITY OF EVENT

All adverse events that do not meet any of the criteria for serious should be regarded as **non-serious adverse events**. Any non-serious adverse event felt to be related to the study device will be captured in the source documents and case report form.

- **Mild** Events require minimal or no treatment and do not interfere with the participant's daily activities.
- **Moderate** Events result in a low level of inconvenience or concern with the therapeutic measures. Moderate events may cause some interference with functioning.
- Severe Events interrupt a participant's usual daily activity and may require systemic drug therapy or other treatment. Severe events are usually potentially life-threatening or incapacitating. Of note, the term "severe" does not necessarily equate to "serious".

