8.3.3.2 RELATIONSHIP TO STUDY INTERVENTION

All adverse events (AEs) must have their relationship to study intervention (device) assessed by the clinician who examines and evaluates the participant based on temporal relationship and his/her clinical judgment. The degree of certainty about causality will be graded using the categories below. In a clinical trial, the study product must always be suspect.

- **Related** The AE is known to occur with the study intervention, there is a reasonable possibility that the study intervention caused the AE, or there is a temporal relationship between the study intervention and event. Reasonable possibility means that there is evidence to suggest a causal relationship between the study intervention and the AE.
- Not Related There is not a reasonable possibility that the administration of the study intervention caused the event, there is no temporal relationship between the study intervention and event onset, or an alternate etiology has been established.

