8.3.4 TIME PERIOD AND FREQUENCY FOR EVENT ASSESSMENT AND FOLLOW-UP

The occurrence of an adverse event (AE) or serious adverse event (SAE) may come to the attention of study personnel during study visits and interviews of a study participant presenting for medical care.

All AEs including local and systemic reactions not meeting the criteria for SAEs will be captured on the appropriate case report form (CRF). Information to be collected includes event description, time of onset, clinician's assessment of severity, relationship to study product (assessed only by those with the training and authority to make a diagnosis), and time of resolution/stabilization of the event. All AEs occurring while on study must be documented appropriately regardless of relationship. All AEs will be followed to adequate resolution.

Changes in the severity of an AE will be documented to allow an assessment of the duration of the event at each level of severity to be performed. AEs characterized as intermittent require documentation of onset and duration of each episode.

At each study visit, the investigator will inquire about the occurrence of AE/SAEs since the last visit. Events will be followed for outcome information until resolution or stabilization.

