8.3.5 ADVERSE EVENT REPORTING

This clinical trial consists of postoperative total knee arthroplasty patients. DRE's common and expected in this group of patients include postoperative pain, nausea, hypotension, anemia, and dehydration. Events anticipated and expected in the postoperative arthroplasty patient will not be considered an adverse event for collection in the eCRF. Additionally, there are no study interventions for the control group. This group will be following the standard of care treatment for a total knee arthroplasty patient. Therefore, no adverse events related to the study will be occurring in this group.

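### The serious-event variable in 9.4.4 has overlapping levels, and conflicting adverse-event capture rules leave the device-related primary safety rate undefined

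*Combined protocol and SAP*

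**What the plan says.** Section 3 lists a primary safety objective and endpoint: "To monitor the study group for any device related adverse events". Section 9.1 likewise gives the primary safety endpoint as events related to the X4 brace, and 10.1.9.1 names device-related events among the data entered in REDCap.

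Section 9.4.4 sets two yes/no variables for patients randomized to the brace. The first is any adverse event versus none, with no mention of relationship. The second is labelled as serious adverse events, and its two levels are "having had one or more adverse events, or not having had any serious adverse events".

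Three sections say which events are recorded:

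- 8.3.3.1: "Any non-serious adverse event felt to be related to the study device will be captured in the source documents and case report form".
- 8.3.4 puts all non-serious events on the CRF and adds: "All AEs occurring while on study must be documented appropriately regardless of relationship".
- 8.3.5 introduces a list of DREs (disease-related events, per the abbreviations in 10.3) that are "common and expected in this group of patients include postoperative pain, nausea, hypotension, anemia, and dehydration". It then says: "Events anticipated and expected in the postoperative arthroplasty patient will not be considered an adverse event for collection in the eCRF".

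Section 8.3.3.2 requires a clinician to judge the relationship of every adverse event to the device.

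**The concern.** A two-level variable should place each patient in exactly one level, and the serious-event variable as worded does not. An endpoint defined on device-related events should also be analysed on device-related events. Whether the any-event variable in 9.4.4 does that depends on what reaches the database, and the capture sections disagree on this.

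At stake is one of the trial's declared primary endpoints. The X4 safety rate could change with the section staff follow when completing the eCRF. A non-serious event caused by the brace, but of a type also common after knee replacement, could be left out of the rate meant to detect it.

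**Working it through.** **Inputs.** The X4 arm has 120 patients (9.2). That figure reproduces: a two-sided two-sample t-test with difference 10, SD 27.5, alpha 0.05 and 80% power needs 119.7 per group, rounded up to 120 (power 0.801). The documents give no adverse-event rates, so every event rate or count below is an assumption used for illustration.

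**Serious-event variable.** Let S be the patients with at least one serious event, N those with only non-serious events, and Z those with none, so S + N + Z = 120.

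- First level as written: S + N.
- Second level as written: N + Z.
- Sum: S + 2N + Z = 120 + N.

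The levels are exclusive only if N = 0. If 10% have any event (12 patients) and 5% a serious one (6), the first level holds 12 instead of 6, six patients sit in both levels, and the total is 126. With any-event rates of 5% to 50% and serious rates of 1% to 5%, N runs from 0 to 120 × (0.50 − 0.01) = 58.8, and the total from 120 to 178.8. With serious inserted, the levels are S and N + Z, which always sum to 120.

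**Capture rules, side by side.**

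| Event in an X4 patient | 8.3.3.1 | 8.3.4 | 8.3.5 |
|---|---|---|---|
| Non-serious nausea, judged unrelated | not required | recorded | excluded from eCRF |
| Non-serious pain, judged brace-related | recorded | recorded | excluded if the second sentence is read literally |
| Non-serious, unexpected, judged unrelated | not required | recorded | not excluded |

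The first row is the direct conflict, between 8.3.4 and 8.3.5. The second row matters most for the endpoint. The sentence in 8.3.5 that does the excluding turns on whether the event is expected, not on its cause, and it carries no exception for events judged device-related. Pain is on the list. An event could therefore be removed by type before the judgement in 8.3.3.2 is made. The third row shows how the any-event variable departs from the endpoint when 8.3.4 is followed.

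**Any event versus device-related.** If 10% to 50% of the arm have any event and 5% to 20% of those patients have a device-related one, the any-event variable counts 12 to 60 patients. The endpoint counts between 120 × 0.10 × 0.05 = 0.6 and 120 × 0.50 × 0.20 = 12.

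**Relationship categories.** Under 8.3.3.2 an event is related if it is a known effect, is reasonably possible, "or there is a temporal relationship between the study intervention and event". It is not related if, among other grounds, "or an alternate etiology has been established". An event that follows brace use and has another established cause meets both definitions.

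**Precision of the X4 proportion.** The exact (Clopper-Pearson) 95% limits for x events in n are the 2.5% quantile of Beta(x, n − x + 1) and the 97.5% quantile of Beta(x + 1, n − x). For n = 120:

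- 0 events: upper limit 1 − 0.025^(1/120) = 3.0%.
- 2 events (1.7%): 0.2% to 5.9%.
- 6 events (5.0%): 1.9% to 10.6%.

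If six patients had brace-related events and four of them were dropped because the event was pain, the report would move from the third line to the second.

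**The case against.** The best defence is that these are drafting matters. Much of it stands, and it limits how far the point goes.

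- A reader might infer that the serious-event table cannot be produced. The bullet's label and its second level both say serious, so there is one plausible reading. The wording is wrong, but the intent is not in doubt.
- A reader might infer that 8.3.3.1 flatly contradicts 8.3.4. It does not say that only device-related events are captured, so the tension is by implication.
- A reader might infer that the any-event variable is wrong whatever else is decided. If only device-related events enter the database, as 8.3.3.1 and 10.1.9.1 suggest, it coincides with the endpoint. The mismatch arises if 8.3.4 is followed.
- The DRE label in 8.3.5 supports a narrower reading in which brace-related pain is not a disease-related event and so is not excluded. That reading is reasonable, but the sentence that excludes events does not repeat the label and rests on expectedness. The dropped event is therefore a possibility under the text, not a certainty.
- 8.3.5 could be read as a carve-out from the term adverse event, leaving 8.3.4 intact. Neither section refers to the other, so staff would have to supply that link themselves.
- A reader might infer that serious device harms would go unreported. The documents do not support that. Section 8.3.2 sends deaths and serious injuries to which the device may have contributed to the IRB, FDA and manufacturer, and 8.3.6 requires a form on unanticipated device effects within 10 working days.
- A reader might call the X4-only scope an error. It matches the declared endpoint in section 3 and the reporting period in 8.3.1, which starts with brace use. The lack of a between-arm safety comparison is a limitation of scope.
- 8.3.3.2 says the device must always be suspect, which leans overlapping cases towards related. It is not stated as a tie-break.

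**Conclusion.** The point holds in this form. The serious-event variable in 9.4.4 is wrong as written, though its intent is plain. Sections 8.3.4 and 8.3.5 conflict directly on expected postoperative events. Because of that conflict, the missing device-relatedness qualifier in 9.4.4 leaves the primary safety rate without a single definition, and a non-serious brace-related event of a listed type could be left out of it.

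No size can be given from the documents; the patient counts above rest wholly on assumed rates. The effect is confined mainly to the eCRF-based safety rate. The efficacy analyses and the sample size of 240 do not change. The wording should be corrected before the safety tables are programmed.

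**What to change.** 1. In 9.4.4, insert serious in the first level of the serious-event variable.
2. Put both variables on the basis used in 9.1: at least one device-related adverse event versus none, and at least one device-related serious adverse event versus none. Qualifying only the first would let a patient with one unrelated serious event count as having a serious event but no adverse event. If an all-cause serious count is wanted, show it in its own labelled row.
3. Report each variable as an X4-arm proportion with an exact 95% confidence interval.
4. Reconcile 8.3.3.1, 8.3.4 and 8.3.5 into one data-capture rule. Relationship should be assessed before any expected-event exclusion applies, and events judged device-related or serious should not be excluded from the eCRF.
5. In 8.3.3.2, state which category applies when an event meets both definitions.

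The cost is wording in five sections, plus a relationship judgement on expected events before they are set aside. No new visits or tests are needed. The downside is that a device-related variable rests on a clinician's judgement, and 6.3 says investigators cannot be blinded; the report should say so.

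Optional, and not part of the error: the Daily Patient Log already records readmission in all patients (4.1, 8.1), so a descriptive table by arm could be added.
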